6.1 Study Time Points

Enrollment Date

A subject's Enrollment Date is defined as the date he or she has met all Part 1 eligibility criteria and the enrollment call in the IXRS system has been completed.

Part 1/Run-in Period

The 24-week period after enrollment and prior to randomization. Specifically, the period begins when a subject initiates treatment with open-label run-in etanercept and/or open-label run-in methotrexate per the eCRF at the same dose he or she was receiving at screening. There are three visits associated with the Run-in Period: Run-in Visit 1, Run-in Visit 2, and Run-in Visit 3.

Run-In Day 1

A subject's Run-In Day 1 is defined as the date of the first dose of IP administration during Part 1.

Run-In Day

A subject's Run-In Day = (Visit Date – Run-In Day 1 date) + 1.

Run-In Failure Date

A subject's Run-In Failure Date is the date the subject ended run-in due to protocol specified criteria per the eCRF.

Randomization Failure Date

A subject's Randomization Failure Date is the date the subject ended run-in due to any reason and was not randomized.

End-of Run-In Date

A subject's End-of Run-In Date is the date subject ends the run-in period per the CRF.

Randomization Date

A subject's Randomization Date is the date when a randomization number is assigned to him or her through the Interactive Voice/Web Response System (IXRS).

Study Day 1

A subject's Study Day 1 is defined as the date of the first dose of IP administration after randomization, or the randomization date if the subject is not dosed.

Baseline

The last measurement for the endpoint of interest taken on or prior to Study Day 1 and after Run-In Visit 3. Hematology and chemistry profiles were not assessed on Day 1; their Run-in Visit 3 values will be used when reporting baseline.

Baseline for Concomitant Medications

Run-In Period Baseline for Concomitant Medications is enrollment date, and Post-Run-In Period Baseline for Concomitant Medications is randomization date.

Study Day

For a given study visit, the study day for a subject is defined as:

Study Day = (Visit Date – Study Day 1 date) + 1.

Part 2/Treatment Period

The up-to 48-week double-blind period beginning with Study Day 1 and ending with the End of Study date.

SDAI Assessment Datea

The SDAI Assessment Date is the latest date of the assessments for Tender Joint Count, Swollen Joint Count, Physician Global Assessment, Patient Global Assessment, and CRP for a given SDAI score.

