10.3.4 Missing and Incomplete Dates

For any listings, missing or incomplete dates will be listed as is. No imputation will be done on incomplete stop date of an adverse event unless specified otherwise.

In the case where the start or stop date of an event or medication is missing or incomplete, the following rule will be applied:

	Missing	Imputation	Exception
Start date (AE, concomitant medication)	Day	01	Default to Study Day 1 if an event starts the same year and month as Study Day 1 and Stop date is after Study Day 1
	Day/Month	01JAN	Default to Study Day 1 if an event started the same year as Day1 and Stop date is after Study Day 1
	Day/Month/Year	No imputation	
Stop date (concomitant medication)	Day	Last day of the month	Default to the End of Study Date or the primary analysis cut-off date for ongoing subjects if the concomitant medication stopped the same year and month as the End of Study Date or primary analysis cut-off date
	Day/Month	31DEC	Default to the End of Study Date or the primary analysis cut-off date for ongoing subjects if the concomitant medication stopped the same year as the End of Study Date or primary analysis cut-off date
	Day/Month/Year	No imputation	

In case a subject dies during the study, impute the missing AE and CM end dates using the subject's date of death.

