11.4 Demographic and Baseline Characteristics

Subject demographic and disease characteristics at enrollment will be summarized descriptively for all subjects in the run-in period.

Subject demographic and baseline disease characteristics at randomization will be summarized descriptively for all subjects in the double-blind treatment period by randomized treatment group.

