11.6.5 Exposure to Concomitant Medication

A summary of all concomitant medications reported may be provided by preferred term as coded by the World Health Organization Drug (WHODRUG) dictionary. Only concomitant medications with a partial or complete end date are tabulated.

12. Changes From Protocol-specified Analyses

Protocol Section 10.5.2 states “Furthermore, the randomized subjects who did not receive any dose of any of the investigational products will also be considered non-responders in the primary analysis.”

However, although subjects may not receive any dose of IP, they may still have an observed SDAI value at week 48. Any randomized subjects with non-missing SDAI at week 48 will be assessed according to their original randomized treatment arm with their observed values.

Changes to Planned Covariates

We modify the listed continuous covariates by dichotomizing them at clinically meaningful cutoffs to demonstrate their influence on the primary endpoint. The following dichotomizations are used:

Age (years): < 65 years, ≥ 65 years

Disease duration: ≤ median, > median; ≤ mean, > mean

Baseline methotrexate dose: <15 mg, ≥15 mg

This dichotomous variable has been added to the pre-specified analysis because when a subject is taken off a biologic, we suspect that subjects on a higher dose of methotrexate at baseline would have a higher probability of SDAI remission than subjects on a lower dose of methotrexate at baseline. The threshold of <15 mg / ≥15 mg was selected based on the minimum and maximum methotrexate doses in this study, 10mg and 25mg, respectively.

Smoking: Never, former, current

This categorical variable has been added to the pre-specified analysis due to recognition of association of poorer arthritis disease activity with smoking.

Maintenance of SDAI remission is the primary endpoint of interest; subgroup analyses shall not be performed on secondary endpoints.

Changes to Analysis Sets

The protocol states that time to recapture SDAI remission and SDAI remission at week 48 will be evaluated for subjects that receive rescue treatment during the double-blind period. This led to the creation of the **Rescue Analysis Set** detailed in [Section 7.4](#).

However, due to the possibility of subjects fulfilling the definition of Disease-Worsening but not receiving rescue therapy, we also added a **Disease-Worsening Analysis Set**, as detailed in [Section 7.3](#).

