Appendix E. Concomitant Medications

The following concomitant medications will be tabulated:

- hydroxychloroquine,
- sulfasalazine,
- minocycline,
- prednisone (5mg daily or less),
- and NSAIDs

The Prednisone dosage of 5 mg daily or less is of interest because entry criteria allows for this dosage.

Only concomitant medications with a partial or complete end date are tabulated.

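### The concomitant-medication table counts only records with an end date, so a listed background RA drug still in use and recorded without a stop date is left out

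*SAP*

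**What the plan says.** SAP 11.6.5 describes an optional summary, by preferred term, covering every concomitant medication reported. The next sentence narrows it: "Only concomitant medications with a partial or complete end date are tabulated". Appendix E closes with the same sentence.

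Appendix E also opens with a firm commitment, "The following concomitant medications will be tabulated", and lists hydroxychloroquine, sulfasalazine, minocycline, prednisone at 5 mg daily or less, and NSAIDs. It explains one entry: "The Prednisone dosage of 5 mg daily or less is of interest because entry criteria allows for this dosage".

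SAP 10.3.4 governs incomplete dates. Where "the start or stop date of an event or medication is missing or incomplete, the following rule will be applied", a stop date lacking the day, or the day and month, is completed. There is a default to the End of Study Date or analysis cut-off "if the concomitant medication stopped the same year and month as the End of Study Date" or cut-off, with a parallel default by year. A stop date missing entirely gets no imputation. The one exception is a subject who dies during the study, for whom the SAP will "impute the missing AE and CM end dates" from the date of death.

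SAP 6.1 defines two period baselines for this purpose: "Run-In Period Baseline for Concomitant Medications is enrollment date, and Post-Run-In Period Baseline for Concomitant Medications is randomization date".

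**The concern.** An end-date filter selects records by whether use has finished, whereas a concomitant-medication table is meant to show whether a drug was taken during the period. Background treatment continued unchanged is the use most likely to have no end date. The wording of Appendix E, in particular tying the prednisone limit to the entry criteria, suggests that background use is what this table is for.

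The stake is descriptive. Two of the three arms are called monotherapy, yet the protocol allows stable sulfasalazine, hydroxychloroquine, minocycline and low-dose prednisone alongside the randomized drugs (Protocol 4.1.1, criteria 109 and 110). Protocol 5.1 mentions no stratification by these drugs, and SAP 4.2 does not name them as covariates. A reader who wants to see how much background treatment each arm carried would look to this table.

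**Working it through.** The plan gives no figure for concomitant-medication use, so there is none to reproduce. The check traces a record through the rules.

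**Step 1: which stop dates pass the filter?** The date rules are from SAP 10.3.4 and the filter from SAP 11.6.5 and Appendix E.

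| Stop date as recorded | Treatment under 10.3.4 | Tabulated? |
|---|---|---|
| Complete | None needed | Yes |
| Day missing | Last day of the month, or the End of Study/cut-off default | Yes |
| Day and month missing | 31 December, or the End of Study/cut-off default | Yes |
| Wholly missing, subject did not die | Not imputed | No |
| Wholly missing, subject died on study | Date of death | Yes, if imputation precedes the filter (order not stated) |

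The End of Study default does not rescue the fourth row. It needs a partial date and a drug that stopped in that month or year. The mention of ongoing subjects there concerns subjects, not ongoing drugs.

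**Step 2: which listed drugs are expected to be ongoing?**

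- Sulfasalazine and hydroxychloroquine: Protocol 6.5.3 requires an unchanged dose throughout, so a compliant user is still taking the drug at the end and has no dose change that would close a record.
- Minocycline: criterion 110 requires stability before run-in; 6.5.3 does not mention it.
- Prednisone: criterion 109 sets the entry limit; Protocol 6.5.2 allows a corticosteroid increase of up to 2 weeks.
- NSAIDs: Protocol 6.5.1 allows reduction, discontinuation and short courses.

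The argument from continued use is therefore firm for two of the five entries and weaker for the other three.

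**Step 3: direction and size.** Take a subject on hydroxychloroquine through run-in and double-blind treatment, 24 + 48 = 72 weeks, with one record and no stop date. That subject adds 0 to the table. A subject with one finished NSAID course, at most 2 weeks under Protocol 6.5.1, adds 1. This shows the direction only.

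In general, let U be the users of a drug who should be counted, and O those among them with no record of that drug that passes the filter. The table shows U − O, and the proportion missed is O/U. The documents give neither quantity, so O/U could lie anywhere from 0 to 1.

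**Step 4: does another output supply the count?** SAP 11.4 says "Subject demographic and baseline disease characteristics at randomization will be summarized descriptively" but does not itemize background drugs. Listings show missing dates as they stand (10.3.4), so the records remain visible but are not counted. No other specified output clearly fills the gap.

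**The case against.** The strongest reply concerns certainty. A reader might infer that every drug in use at study end is omitted. The documents do not support that. Protocol 6.5 lists a stop date among the items collected but does not say how an ongoing drug is entered, and the concomitant-medication eCRF page is not shown. If sites entered a closing date for every ongoing drug, nothing would be lost. This stands, and the point is conditional on a blank stop date.

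Second, the filter acts on records, not subjects. A user with one closed record of a drug is still counted for it. Dose changes in prednisone or NSAIDs could create closed records, though the documents do not say that sites close a record at a dose change. This also stands. It removes any claim that the table would consist mostly of people who stopped, and any percentage for the shortfall would only restate an assumption.

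Third, the table is optional in 11.6.5, the analysis methods in Protocol 10.5 specify no concomitant-medication analysis, and no test uses it. The underlying data survive in the on-study records, the RA medication history (Protocol 7.3.4) and the listings. This limits the weight of the point but does not answer it. Appendix E commits to tabulating these drugs, and a table that is produced should match its stated scope.

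**Conclusion.** The rule is wrong as written. Followed exactly, it drops any record with a wholly missing stop date unless the subject died. That conflicts with the scope stated just before it in 11.6.5 and with the commitment in Appendix E.

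On the assumption that at least some ongoing drugs carry no stop date, the table understates use of the listed background drugs by an amount that cannot be estimated from the documents. The case is clearest for compliant users of sulfasalazine and hydroxychloroquine with no earlier closed record.

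The matter is minor. A reader might infer that the efficacy comparison is compromised, but nothing supports that: the primary test, alpha and sample size do not depend on this table.

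**What to change.** Delete the end-date sentence in SAP 11.6.5 and in Appendix E. In its place, count every medication whose use overlaps the period, using the baselines already in SAP 6.1:

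- **Run-in:** from the enrollment date to randomization, or to the End-of Run-In Date for subjects not randomized.
- **Post-run-in:** from the randomization date to the last contact at which concomitant medications are collected. The SAP should name that contact: Protocol 6.5 collects to end of study, but Table 1 last schedules this item at Week 48/ET, and the follow-up call is for serious adverse events.
- **Wholly missing end date:** include the record if it is marked ongoing or was reported as in use at or after the period's baseline. Do not count a history-only record with an unknown stop date and no evidence of on-study use; show it in the listing. Without this distinction, an old RA drug with a forgotten stop date could be counted as current.
- **Wholly missing start date:** classify the record by its stop date or by reported on-study use.

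Leave the rest of 10.3.4 unchanged.

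The cost is SAP wording and a little programming. Start and stop dates are already collected (Protocol 6.5). The one thing to confirm is whether the eCRF has an ongoing indicator; if not, the rule relies on reported on-study use.

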Appendix B. Code Fragments

Appendix C. Reference Values/Toxicity Grades

Adverse event severity is graded based on the National Cancer Institute Common Toxicity Criteria for Adverse Events (CTCAE) version 4.0.

Laboratory toxicity is graded based on the National Cancer Institute Common Toxicity Criteria (CTC) version 2.0 with the following additions:

	Grade				
	0	1	2	3	4
BUN	WNL	>1.5 – 2.0 x ULN	>2.0 – 3.0 x ULN	>3.0 – 4.0 x ULN	>4.0 x ULN
HGB	WNL	>ULN	>(ULN+1) – (ULN+2)	>(ULN+2)	-
Urine Protein	NEG, NEGATIVE, TRACE, NORMAL, NOT DETECTED	+, +1, 1+	++, +2, 2+, +++, +3, 3+	++++, +4, 4+	-
Platelet Count	WNL	> ULN – 1.0x10 ¹² /L	> 1.0x10 ¹² /L	-	-
Leukocyte Count	WNL	> ULN – 2.0x10 ¹⁰ /L	> 2.0x10 ¹⁰ /L – 4.0x10 ¹⁰ /L	> 4.0x10 ¹⁰ /L	-

Appendix D. Patient-reported Outcome Forms/Instruments

Scoring Algorithm of Health Assessment Questionnaire Disability Index (HAQ-DI)

All language versions will use the following scoring system.

- HAQ-DI scores range from 0 (no difficulty) to 3 (much difficulty) for each of the 20 questions in the 8 categories.
- Calculate the maximum score for each of the 8 categories. At least one question in each category needs to be answered to compute the maximum score.
- If an aid or device is used or help from another person is needed, adjust the score for the associated category by increasing a zero or a 1 to a 2. If a patient's highest score for that category is a 2, it remains a 2, and if a three, it remains a three.

Sub-domain	Aids or devices
Dressing & Grooming	Devices used for dressing (button hook, zipper pull, long-handled shoe horn, etc.)
Arising	Special or built up chair
Eating	Built up or special utensils
Walking	Cane, Walker, Crutches, Wheelchair
Hygiene	Raised toilet seat, Bathtub seat, Bathtub bar, Long-handled appliances in bathroom
Reach	Long-handled appliances for reach
Grip	Jar opener (for jars previously opened)
Activities	N/A

If no more than 2 categories have missing scores, then the disability score is the mean of the non-missing category scores (the summed category scores divide by the number of categories answered). Otherwise, the disability score is set to missing.

Appendix E. Concomitant Medications

The following concomitant medications will be tabulated:

- hydroxychloroquine,
- sulfasalazine,
- minocycline,
- prednisone (5mg daily or less),
- and NSAIDs

The Prednisone dosage of 5 mg daily or less is of interest because entry criteria allows for this dosage.

Only concomitant medications with a partial or complete end date are tabulated.
